NCT03966573

Title: «Evaluation of physical function, Quality of Life and Hip- and Knee Osteoarthritis Minimum 15 years After femoral Lengthening».

Date: 01.06.2018

Introduction

Limb lengthening is an established method for treatment of leg length discrepancy (anisomelia) or short stature (Castelein & Docquier, 2016; Steen, Terjesen, & Bjerkreim, 1997). The most common cause of limb lengthening is anisomelia (Castelein & Docquier, 2016). Anisomelia can either be innate or acquired, for instance after an injury (Castelein & Docquier, 2016). At Oslo University Hospital, it is performed 15-20 lower extremity lengthening procedures yearly including tibial and femoral lengthening. The vast majority of these are performed on patients with congenital deformities or other skeletal pathologies, and only a few are without a clear diagnosis or with acquired leg length discrepancy. Leg length discrepancy can be problematic as it often causes pelvic tilt towards the short side (Steen et al., 1997). This again, can cause functional scoliosis, largely affecting the gait (Steen et al., 1997). It is documented that anisomelia of more than two cm should be treated (Steen et al., 1997). Treatment could be either conservative by using shoe lift or surgical, where the long leg could be shortened or the short leg lengthened (Steen et al., 1997). In growing children there's also the possibility to stop growth in the long leg at a certain time to achieve leg length equality (isomelia) (Steen et al., 1997). In many patients, limb lengthening will of various reasons be preferred, if the discrepancy is over three cm (Steen et al., 1997).

There are described several limb lengthening methods, for instance the Wagner method and the Ilizarov technique (Ilizarov, 1988; Wagner, 1971). The callotasis principle (distraction osteogenesis or callus distraction) described by Gavril A. Ilizarov is the most trusted and accepted method (Castelein & Docquier, 2016; Paley, 1990), and all patients invited to participate in this project are lengthened with callotasis. With the callotasis method the bone is stabilized at least two places with a fixator before the surgeon makes a corticotomy between the fixations (Ilizarov, 1988). Bone and soft tissue are lengthened by regeneration under conditions of tension stress when the bone fragments on each side of the corticotomy is pulled apart, usually 0.75 - 1 mm a day distributed over three to four sequences until goal of lengthening is achieved (Ilizarov, 1988; Maffulli, Pattinson, & Fixsen, 1993; Paley, 1990).

In our study we will concentrate on femoral lengthening as it appear more homogenous than tibial regarding healing and complications (Maffulli et al., 1993). In addition, unlike tibia, femur has large two-joint muscle groups surrounding it (Maffulli et al., 1993), making it more relevant for us investigating adjacent joint function than with tibial lengthening. Most patients regain full range of motion in their hip and knee after femoral lengthening with callotasis (Barker, Simpson, & Lamb, 2001; Bhave et al., 2017; Herzenberg, Scheufele, Paley, Bechtel, & Tepper, 1994; Holm, Steen, Ludvigsen, & Bjerkreim, 1995; Horn, Grimsrud, Dagsgard, Huhnstock, & Steen, 2015; Kawoosa, Majid, Halwai, Mir, & Mir, 2004; Maffulli, Nele, & Matarazzo, 2001; Motmans & Lammens, 2008; Zambito & Aldegheri, 1997). However, limb lengthening is associated with high risk of complications, where loss of knee extension is most commonly reported (Fitch, Thompson, Rizk, Seaber, & Garrett Jr, 1996; Paley, 1990). Infections, subluxation of the hip- or knee joint, premature healing, lack of healing, development of deformities after fixator removal, fractures after conclusion of lengthening, reduced gross motor skills and more pain than healthy controls are other known complications associated with limb lengthening (Castelein & Docquier, 2016). We have found studies both indicating muscle weakness, and unchanged muscle strength after femoral lengthening with callotasis (Bhave et al., 2017; Holm et al., 1995; Krieg, Gehmert, Neeser, Kaelin, & Speth, 2018; Oey, Engelbert, & Wieneke, 1999). These are all small studies with different design and patient basis, making them hard to compare. Some studies report good functional outcome after femoral lengthening, but the measurement of function is poorly defined and described in these studies (Eralp, Bilen, Dikmen, & Eren, 2012; Zambito & Aldegheri, 1997). We have only found two studies describing health status and quality of life after femoral lengthening with callotasis. Shahcheraghi et al. (2015) found no deterioration regarding function, quality of life and health status comparing pre- and postoperative status, while Moraal et al. (2009) found that patients had physical limitations, but normal psychosocial function and self-esteem compared to healthy normal population. Quality of life were comparable to healthy normal population, except from significantly lower gross motor function, vitality, and more pain. There is lack of research on physical function, quality of life, health status and activity level after femoral lengthening with an obvious need for further research with good statement of both patient group and method.

Textbooks describing limb lengthening claims that it increases the risk of osteoarthritis (Sneppen, Bünger, Hvid, & Søballe, 2014), but to our knowledge this statement lacks research evidence and appears more like an assumption. Animal research have shown tendencies of knee osteoarthritis after femoral lengthening (Stanitski, 1994), but we have only succeeded in finding one article that describes osteoarthritis development after femoral lengthening on humans, where 18 out of 23 patients showed knee osteoarthritis with a mean follow-up of 6 years after femoral and / or tibial lengthening (Jeong, Inan, Riddle, Gabos, & Bowen, 2006).

It is an interesting finding, but this study used another lengthening method than today's gold standard of callotasis and were performed on patients with congenital femoral deficiency. It is hard to say if the osteoarthritis seen in these patients is in context with the lengthening procedure with their method of choice or the patient's pathology. It is important to know if the procedure itself increases the risk of developing osteoarthritis. In our study we will therefore only include patients with idiopathic or acquired leg length discrepancy, minimizing as far as we can the risk of the patient's pathology being the explanatory factor for eventual findings. Socioeconomically it's relevant to know whether limb lengthening increases the risk of osteoarthritis, as the condition leads to pain and reduced function, and can cause considerable costs regarding sick leaves, medications, physiotherapy and possibly prosthetic operations (Bitton, 2009; Grotle, Hagen, Natvig, Dahl, & Kvien, 2008). It can take time from an initial factor until osteoarthritis can be confirmed by conventional radiology, and all the research we have been able to find describing consequences of limb lengthening, all have relatively short follow-up, mostly far below ten years. With the lack of research available in the question of context between limb lengthening and risk of osteoarthritis, there is an obvious need for more research to investigate this with long enough follow-up to be able to identify osteoarthritis within the patient group.

There is of considerable value to both patients and treating health professionals to be aware of what long term consequences to expect after limb lengthening when operative or conservative strategy of treatment is to be decided. Based on this, we want to evaluate physical function, quality of life and development of hip- and knee osteoarthritis minimum 15 years after femoral lengthening due to idiopathic or acquired leg length discrepancy.

Responsibility and sponsorship

Oslo University Hospital is responsible for the study, and Sophies Minde AS has sponsored the project by granting a research scholarship paying the salary for the researcher to be able to implement this study. All data will be collected at Oslo University Hospital. Radiologic examinations will be performed by radiographic section at Oslo University Hospital, while all other data will be collected by the researcher.

Purpose of the study and research questions

The purpose of this study is to evaluate physical function (range of motion, 30 seconds sit to stand test, stair test and hop tests), quality of life, health status, activity level and development of osteoarthritis in the hip- and knee joint minimum 15 years after femoral lengthening due to idiopathic or acquired leg length discrepancy.

Research questions:

- 1. Are there differences in physical function in the lower extremities in patients who have undergone femoral lengthening compared to reference values?
- 2. Do patients who have undergone femoral lengthening achieve recommendations for physical activity?
- 3. Are there differences in quality of life in patients who have undergone femoral lengthening compared to reference values?
- 4. Are there differences in health status in patients who have undergone femoral lengthening compared to reference values?
- 5. Are there differences in development of osteoarthritis in lengthened and unlengthened hip- and knee joint in patients who have undergone femoral lengthening?

Design, material and method

This study is a quantitative cross-sectional study.

Patients

Includable patients for this study will be identified from protocols from the surgical department.

Inclusion criteria: Patients with idiopathic (unknown cause) or post traumatic leg length discrepancy, that has been operated with femoral lengthening with callotasis minimum 15 years ago.

Exclusion criteria: Innate skeletal pathology leading to shortening of the lower extremity, malangulation and less developed musculature, such as congenital femoral deficiency (CFD) or fibular hemimelia (Jeong et al., 2006). Patients with acquired leg length discrepancy after

infection in hip- or knee joint, and patients that have inserted hip- or knee prosthesis will also be excluded.

Data collection

All examinations will be completed at the same day at Oslo University Hospital.

Outcome measures

Physical function

Active range of motion (AROM) of the hip- and knee joint will be measured in degrees with an analog goniometer. Even though goniometric measures have uncertainties, acceptable intra-tester reliability is shown in hip and knee measurements with analog goniometer (Holm et al., 2000; Watkins, Riddle, Lamb, & Personius, 1991).

30 seconds sit to stand test (30sSTS) measures lower extremity strength (Bennell, Dobson, & Hinman, 2011; Csuka & McCarty, 1985). Chair with height of 44-45 cm will be used. The participant is told to sit and stand as many times as possible within 30 seconds, and the total number is registered (Tveter, Dagfinrud, Moseng, & Holm, 2014).

Stair test measures submaximal cardiopulmonary endurance (Cataneo & Cataneo, 2007). The participant is asked to move as fast as possible 18 stairs $(17\pm1 \text{ cm})$ up and down three consecutive times. Total time in seconds is registered. The participant is allowed to run and use the banister if needed. The participant has to step on every stair. Pulse is measured, and Borg scale 6-20 registered immediately after the test (Tveter et al., 2014).

Hop tests will be used to compare function in the lengthened and unlengthened limb. The tests are developed for patients with ACL ruptures, but the high specificity and low false positive rates found is an argument for us to use it to separate the limbs from each other and confirm if there is impaired lower limb function (Noyes, Barber, & Mangine, 1991). Single hop for distance, triple hop for distance, timed hop (seconds used to hop 6 m) and cross-over hop for distance (triple cross-over hop over 15 cm wide tape) will be performed on both legs.

Questionnaires

Knee Osteoarthritis Outcome Score (KOOS) is a self-administered questionnaire. It has shown validity and reliability measuring function and pain in patients with knee injuries and osteoarthritis (Roos & Lohmander, 2003; Roos, Roos, Lohmander, Ekdahl, & Beynnon, 1998). The participant answer questions regarding pain, function, stiffness and quality of life regarding knee pain.

EQ-5D-5L has shown validity and reliability measuring health related quality of life in patients with hip- and knee pain (Fransen & Edmonds, 1999). It is a self-administered questionnaire where the participants report the extent of problems they have in the five dimensions mobility, self-care, usual activities, pain/discomfort and anxiety/depression. The questionnaire also contains a vertical analogue scale with the labelled endpoints 0-100 giving a valuation of the participants own health state that can be used as a quantitative measure of health outcome based on the patients' own judgement. The use of this questionnaire is approved by EuroQol.

International Physical Activity Questionnaire (IPAQ) short version has shown validity and reliability, and is a self-administered questionnaire used to obtain estimates of physical activity level (Cerin et al., 2016). Participants answer the amount of time being in vigorous activity, moderate activity, walking and sitting during the last 7 days. This will be transitioned into MET-score.

Radiology

Osteoarthritis in hip- and knee joints will be evaluated by measuring joint space width (JSW) and Kellgren & Lawrence classification (KL) (Terjesen & Gunderson, 2012). Leg length equality will be evaluated with standing axis measurements. All radiologic measurements are done by an experienced radiologist at Oslo University Hospital. Lengthened side will be compared to unlengthened side.

Analyzes

AROM in the hip and knee joint: The lengthened and unlengthened side will be compared using to-sample t-test.

30Ssts: We will analyze if there is a difference between patients that have undergone femoral lengthening and reference values with Wilcoxon signed ranks test (Tveter et al., 2014).

Stair test: We will analyze if there is a difference between patients that have undergone femoral lengthening and reference values with Wilcoxon signed ranks test.

Hop tests: The results will be analyzed comparing lengthened and unlengthened side using Wilcoxon signed ranks test.

KOOS: To analyze if there is a difference between patients that have undergone femoral lengthening and reference values, one-sample t-test will be used.

EQ-5D-5L: We will analyze if there is a difference between patients that have undergone femoral lengthening and reference values with one-sample t-test

IPAQ: To analyze if the patients meet recommendations for physical activity of 600 MET, one-sample t-test will be used (ASCM, 2013).

JSW and KL: Evaluation of osteoarthritis development in the lengthened and unlengthened side will be presented by descriptive statistics.

Research ethics assessment

Possible negative consequences of this project are that the participants will have to use their time without being economically compensated, and they will be exposed to x-rays that are not medically induced. On the other hand, the participants are offered a thorough examination of their hips and knees, both clinically and radiological, in addition to participate in research that may be beneficial for other patients going through the same procedure.

Usefulness

The aim of the study is to increase knowledge about function, quality of life and risk of developing osteoarthritis after femoral lengthening. it is of importance for both patients and clinicians to be aware of possible long-term consequences of the treatment. All patients that

are treated with femoral lengthening at Oslo University Hospital nowadays, are close monitored by physiotherapist first in hospital care, and then locally after discharge. As there is lack of available research on the field, our results can be of interest for both patients, orthopedists, physiotherapists and other health care professionals.

Approvals and registrations

- Regional ethics committee: 2018/416 REK South East B.
- Data protection officer at Oslo University Hospital: 18/08589.
- Radiographic section at Oslo University Hospital: 1829.
- ClinicalTrials.gov: NCT03966573.

Reference list

- American College of Sports Medicine. (2013). ACSM's health-related physical fitness assessment manual: Lippincott Williams & Wilkins.

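### No masking of the radiologist to the operated side is described for KL and JSW, so a side-dependent reading error would pass straight into the answer to research question 5

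*Combined protocol and SAP*

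**What the plan says.** The fifth research question asks: "Are there differences in development of osteoarthritis in lengthened and unlengthened hip- and knee joint in patients who have undergone femoral lengthening". The Radiology section names the measures: "Osteoarthritis in hip- and knee joints will be evaluated by measuring joint space width (JSW) and Kellgren & Lawrence classification (KL"). It adds a third reading from the same examination: "Leg length equality will be evaluated with standing axis measurements". One sentence then covers all three, and the next gives the contrast of interest: "All radiologic measurements are done by an experienced radiologist at Oslo University Hospital. Lengthened side will be compared to unlengthened side".

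The Analyzes section says that JSW and KL will be summarised descriptively by side. It names no test for them.

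The section on responsibility and sponsorship has the hospital's radiographic section perform the x-ray examinations, while the researcher collects everything else.

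The document does not mention masking of the reader to side or history, joint-only images, reading order, repeat reading or reader agreement.

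**The concern.** KL grading needs judgement, and a JSW value depends on where the reader places the measurement. Both can shift with what the reader knows about the joint. As described, the radiologist may know which limb was lengthened, either from the history or from the standing-axis film. The plan has nothing that keeps this knowledge away from the joint grading.

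Question 5 is the part of the study that addresses whether lengthening is followed by more osteoarthritis. Its answer will be a pair of side-specific summaries. A reading habit that is the same on both sides does little harm in such a comparison. One that differs between the sides would appear as a side difference, or hide one.

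**Working it through.** **Inputs.** The documents give no sample size, expected prevalence, standard deviation, test or power for KL or JSW, so there is no stated figure to reproduce. From the documents I take the within-patient contrast (Research questions, 5), the two measures and the reader (Radiology), and the descriptive presentation (Analyzes). The values of p, s, t and n below are assumptions chosen to show scale.

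**1. Is masking provided anywhere?** The Radiology section says who measures and what is compared. The Analyzes section says how results are presented. The responsibility section separates the radiographic section from the researcher. That division of roles keeps the reading apart from the clinical data collection, but it does not keep the operated side from the reader. No other section bears on the question.

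**2. JSW.** Let L and U be the true widths on the lengthened and unlengthened sides of one patient.

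- Same error c on both sides: (L + c) − (U + c) = L − U, so the error cancels.
- Error b on the lengthened side only: (L + b) − U = (L − U) + b. The mean side difference moves by exactly b mm, whatever the sample size.

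**3. KL grade 2 or higher.** Let the true prevalence be p on both sides, and let the reader upgrade a share s of truly negative lengthened joints.

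- Observed prevalence, lengthened side: p + s(1 − p)
- Observed prevalence, unlengthened side: p
- Spurious difference: s(1 − p)

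For p = 20% and s = 5%: 0.20 + 0.05 × 0.80 = 0.24.

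| Assumed p | s = 5% | s = 10% | s = 15% |
|---|---|---|---|
| 10% | 14.5% (ratio 1.45) | 19.0% (1.9) | 23.5% (2.35) |
| 20% | 24% (1.2) | 28% (1.4) | 32% (1.6) |
| 30% | 33.5% (1.12) | 37% (1.23) | 40.5% (1.35) |

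Each cell is the observed prevalence on the lengthened side, and the ratio is to the true value p.

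**4. In joints.** At p = 20% and s = 10%, the expected number of spuriously positive lengthened joints of one type is n × 0.10 × 0.80. That is 1.6 for an assumed 20 patients and 3.2 for an assumed 40.

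**5. Direction.** A reader who leaned the other way and downgraded a share t of truly positive lengthened joints would subtract t × p. At t = 10% and p = 20% that is 0.10 × 0.20 = 2 percentage points. The formulas show how an error would travel. They do not show that one occurs, or in which direction.

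**The case against.** The strongest reply is that the plan is silent on masking, which is not the same as stating an unmasked reading. This stands: nothing says that the radiologist is told the operated side or the history, and masking may already be local practice.

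A reader might infer that the radiologist expects osteoarthritis on the lengthened side, because the Introduction says "Textbooks describing limb lengthening claims that it increases the risk of osteoarthritis". The same sentence goes on to say that the claim lacks evidence and looks like an assumption. The Introduction then questions whether the one human study it found reflects the lengthening or the patients' underlying condition. No expectation is attributed to the radiologist, so this does not establish a direction of bias.

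A reader might also want a false-positive rate for JSW. The plan has no JSW test and no sample size, so such a rate would not describe it. What can be said is that a shift of b mm enters the mean difference in full.

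Nor does it follow that the error could never be found because the analysis is descriptive. A hypothesis test would not reveal reader bias either, and a later masked re-reading of stored images could.

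Some features of the plan help. The reader is an experienced radiologist and not the researcher, and if one person reads both sides, differences between readers do not enter the side contrast. How recognisable the operated femur is after 15 years or more is not documented, so that it may be seen on the standing-axis film is a possibility, not a fact. None of this removes the point, because none of it separates joint grading from knowledge of side.

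**Conclusion.** The point holds in this form: no masking of the reader to operated side or history is described, no order is set between joint grading and the standing-axis reading, and the comparison they feed is one in which a side-dependent error does not cancel.

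The harm at stake is a biased descriptive estimate, not an inflated type I error. Under the assumed values (p from 10% to 30%, s from 5% to 15%), the spurious difference in KL prevalence runs from 0.05 × 0.70 = 3.5 to 0.15 × 0.90 = 13.5 percentage points. These figures illustrate the mechanism and do not estimate the bias in this study. The documents do not support the stronger conclusion that the readings are known to be unmasked or tilted towards the lengthened side.

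The change is a cheap improvement that should be made before the films are read.

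**What to change.** Add a short reading procedure to the Radiology section:

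- Someone other than the radiologist exports each hip and knee as a separate image cropped to the joint, without the femoral shaft, and keeps the original scale so that JSW can still be measured.
- Identifiers and side markers are removed, all images are mirrored to one side, and joints are presented in random order under a code.
- The same radiologist grades KL and measures JSW on these images, masked to history and operated side, and locks the readings before opening the standing-axis films.
- The radiologist records each image on which the operated side is still evident. The descriptive side comparison is reported for all joints and repeated without those images.

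If the readings are already masked in practice, a sentence saying how is enough.

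The cost is a few hours of image preparation. No extra reader, x-ray or visit is needed. The limitation is that masking will be incomplete where hardware or deformity lies close to the joint. The record of recognisable images shows how often that happened.

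### Range of motion in the two legs of the same patient is to be compared with an independent two-sample t-test, although the data are paired

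*Combined protocol and SAP*

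**What the plan says.** The section headed Analyzes gives one sentence on range of motion: "AROM in the hip and knee joint: The lengthened and unlengthened side will be compared using to-sample t-test". The test name is misspelt, and two-sample is the natural reading. The outcome is continuous: "Active range of motion (AROM) of the hip- and knee joint will be measured in degrees with an analog goniometer" (Outcome measures, Physical function).

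Three other statements fix the data structure:

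- Design, material and method: "This study is a quantitative cross-sectional study".
- Eligibility, in the Patients section: "Patients with idiopathic (unknown cause) or post traumatic leg length discrepancy, that has been operated with femoral lengthening with callotasis minimum 15 years ago". No control group is described.
- Data collection: "All examinations will be completed at the same day at Oslo University Hospital".

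For the hop tests, which make the same contrast between sides, the plan says: "The results will be analyzed comparing lengthened and unlengthened side using Wilcoxon signed ranks test". KOOS, EQ-5D-5L and IPAQ are each assigned a one-sample t-test. The document mentions no paired t-test, within-patient difference or mixed model for range of motion.

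**The concern.** The two samples are the two legs of the same people. An independent-groups test ignores that link and computes its standard error as if the legs belonged to different patients. Legs of one person share age, sex and build, so their joint motion should be positively correlated. The test is then conservative and a real side difference is easier to miss.

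Range of motion is the first component of physical function listed in the study purpose, and the Introduction names loss of knee extension as the complication most often reported after lengthening. A non-significant result from the wrong test could be read as reassurance on that question. More recruitment is unlikely to make up the lost precision. The Introduction reports 15-20 lower-limb lengthenings a year at the hospital, tibial ones included, and says only a few are in patients with acquired discrepancy or no clear diagnosis.

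**Working it through.** **Inputs.** From the document: one cohort, both sides measured in each patient on the same day, outcome in degrees, test named as a two-sample t-test. The document does not give the number of patients n, the significance level, the SD, the expected side difference or the between-leg correlation ρ, so there is no figure of the plan's own to reproduce. Everything below is illustrative: n = 10 to 30, two-sided 5% level, true side difference 0.5 SD, bivariate normal data.

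**Standard errors.** With the same SD s on both sides:

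- two-sample: SE = s·√(2/n)
- paired: SE = s·√(2(1−ρ)/n)
- ratio: 1/√(1−ρ), which is 1.20 at ρ = 0.3, 1.41 at 0.5 and 1.83 at 0.7.

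**Confidence interval, example.** Assume s = 10 degrees and n = 30.

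- Two-sample: t(0.975, 58) × 10 × √(2/30) = 2.002 × 2.582 = 5.2 degrees either side.
- Paired, ρ = 0.3: t(0.975, 29) × 10 × √(1.4/30) = 2.045 × 2.160 = 4.4 degrees.
- Paired, ρ = 0.5: 2.045 × 10 × √(1/30) = 2.045 × 1.826 = 3.7 degrees.
- Paired, ρ = 0.7: 2.045 × 10 × √(0.6/30) = 2.045 × 1.414 = 2.9 degrees.

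**Power and type I error, equal SDs** (simulation, 100,000 datasets per setting):

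| n | ρ | Power, two-sample | Power, paired | Actual size of the nominal 5% two-sample test |
|---|---|---|---|---|
| 10 | 0.3 | 15% | 22% | 2.3% |
| 10 | 0.5 | 12% | 29% | 1.0% |
| 10 | 0.7 | 8% | 45% | 0.2% |
| 20 | 0.3 | 31% | 43% | 2.1% |
| 20 | 0.5 | 28% | 56% | 0.8% |
| 20 | 0.7 | 24% | 78% | 0.1% |
| 30 | 0.3 | 48% | 61% | 2.0% |
| 30 | 0.5 | 47% | 75% | 0.7% |
| 30 | 0.7 | 47% | 93% | 0.1% |

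The paired test held its size at about 5% throughout.

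**Where the direction changes.** The two-sample interval has more degrees of freedom, so at ρ = 0 it is slightly the narrower (width ratio 0.97 at n = 20). The widths are equal when ρ = 1 − [t(0.975, 2n−2)/t(0.975, n−1)]², which is 0.14 at n = 10, 0.06 at n = 20 and 0.04 at n = 30. At ρ = −0.2 and n = 20 the two-sample test rejects too often, with actual size 7.2%.

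**Unequal SDs.** Only one leg was operated on, so the lengthened side may vary more. With SDs s₁ and s₂ the ratio of standard errors is √[(s₁² + s₂²)/(s₁² + s₂² − 2ρs₁s₂)]. At ρ = 0.5 and SDs 2:1 this is √(5/3) = 1.29. At 3:1 it is √(10/7) = 1.20. With n = 20, a difference of 0.5 SD and the average variance held fixed, power (two-sample against paired) is:

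- 2:1, ρ = 0.3: 32% against 40%
- 2:1, ρ = 0.5: 30% against 49%
- 3:1, ρ = 0.3: 33% against 38%

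**The case against.** The strongest reply is that the wording is a slip. The test name is misspelt, the plan nowhere says independent or unpaired, and the hop-test sentence suggests that the authors know the sides are paired. They may have meant a paired-samples t-test. That is possible, but the text does not say it. The plan names one-sample t-tests elsewhere, so it does distinguish types of t-test, and an analyst following this sentence would run the independent version. The wording has to change under either reading. It is also fair to say that the hop-test sentence is weak evidence of a deliberate view on pairing, because the plan uses the same Wilcoxon test against reference values for the sit-to-stand and stair tests. The pairing follows from the design without it.

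The second reply concerns size, and it largely stands. No correlation, SD or sample size is documented. At ρ = 0.1 with n = 20 and equal SDs, power is 33% against 35%, which is hardly a loss, and unequal SDs shrink the gap further. Too wide an interval and lost power both depend on ρ exceeding a small break-even value.

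The third reply concerns importance. The mean side difference does not change when every patient has both sides measured. With positive correlation the error is conservative and creates no false claim of harm. No primary outcome is named, range of motion is one of several function measures, and research question 1 compares function with reference values. These points are correct and limit the consequences. They do not make the independent-groups test suitable for paired data.

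**Conclusion.** The concern holds. As written, the plan applies an independent-groups test to the two legs of the same patients, and nothing else in the document supplies a paired method for range of motion. That conclusion follows from the design and does not depend on any assumed number.

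The size of the loss does depend on assumptions. For a true difference of 0.5 SD, n between 10 and 30, equal SDs and ρ between 0.3 and 0.7, the two-sample test gives up roughly 7 to 54 percentage points of power, and its standard error is 1.2 to 1.8 times the paired one. The loss nearly disappears at ρ near 0.1 and is smaller when the lengthened side is more variable. Positive correlation is the expected case for two legs of one person, but the document does not establish it. The error affects the p-values and confidence intervals. It does not bias the estimated side difference when pairs are complete. It must be corrected because the named test does not fit the design and correcting it is practically free.

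**What to change.** Replace the range-of-motion sentence in the section headed Analyzes with, for example: *For each hip and knee motion, the within-patient difference (lengthened minus unlengthened side) will be analysed with a paired t-test and reported as a mean difference with 95% CI. If the differences are clearly non-normal, the Wilcoxon signed ranks test will be used, as for the hop tests.*

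If a paired test was intended all along, the same sentence makes that clear. The cost is one sentence of wording. No further patients, visits or measurements are needed, and no stated sample size or power changes, because the document gives none.
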